- Urine (midstream specimen) for urinalysis, bacterial culture and pregnancy test (if participant is of child bearing potential) will be collected.
- Review of any changes in concomitant medications.
- Reporting of any adverse events or changes in health status.
- Receive oral and written instructions for participant weekly diary use.
- Participants will receive 3 month (90 day) supply of Uromune® treatment and be given instructions on administration of study treatment. The participant will administer first dose of study treatment during this visit.
- Review of any adverse events after study treatment administration.

Participant Follow-Up:

3 Month Clinic Visit (90 days +7 from Baseline Visit):

Participants will return to the clinic for a predetermined visit following the three month (90 day) vaccine administration. During this visit participants will undergo:

- Completion of Quality of Life Questionnaire (SF-12) and Satisfaction Questionnaire prior to any other study procedures.
- Vitals (blood pressure and heart rate), height and weight.
- Urine (midstream specimen) for urinalysis, bacterial culture and pregnancy test (if participant is of child bearing potential) will be collected.
- Return of study treatment bottle.
- Diary compliance check and return of treatment period diary.
- Vaccine compliance check. This will be conducted through a review of the participant's diary.
- Reporting of any adverse events or changes in health status.
- Review of any changes in concomitant medications.
- Review of UTI history including symptoms, number of diagnosed UTIs, review of cultures performed, bacteria responsible for UTI and any treatments participant has received over the preceding 3 month period (If the participant has reported a UTI, all efforts will be made to complete the CRF with documentation of physician notes and/or culture reports if available).
- Instructions on how to complete the post treatment symptom diary.

6 Month Phone Call (+/- 7 days):

Participants will be contacted by phone 6 months after their baseline visit and asked about the following:

- Diary compliance check to ensure participant has been completing their symptom diary.
- Reporting of any adverse events and a check of health status.
- Review of any changes in concomitant medications.

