- Vitals (blood pressure and heart rate), height and weight.
- Reporting of any adverse events.
- Reporting of changes in concomitant medications.
- Diary compliance check.
- Study treatment compliance check (only if unscheduled visit occurs during the 90 day treatment period).
- Review of UTI history including symptoms, number of diagnosed UTIs, review of cultures performed, bacteria responsible for UTI and any treatments participant has received over the preceding 3 month period (If the participant has reported a UTI, all efforts will be made to complete the CRF with documentation of physician notes and/or culture reports if available).

Early Termination:

If the study is stopped early based on planned protocol interim analysis and/or stopping rules or if the participant withdraws from the study every effort should be made to bring the participant in for an Early Termination Visit. At this visit the participant will undergo the following:

- Completion of Quality of Life Questionnaire (SF-12) and Satisfaction Questionnaire prior to other study procedures.
- Vitals (blood pressure and heart rate), height and weight.
- Urine (midstream specimen) for urinalysis, bacterial culture and pregnancy test (if participant is of child bearing potential) will be collected.
- Diary compliance check and return of treatment period diary or post treatment period diary depending on timing of visit.
- Reporting of any adverse events and a check on health status.
- Review of any changes in concomitant medications.
- Review of UTI history including symptoms, number of diagnosed UTIs, review of cultures performed, bacteria responsible for UTI and any treatments participant has received over the preceding 3 month period (If the participant has reported a UTI, all efforts will be made to complete the CRF with documentation of physician notes and/or culture reports if available).
- Vaccine compliance check and return of study treatment bottle (only if visit occurs during the 90 day treatment period).

Specimen Collection and Procedures:

Midstream urine specimen:

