Temperature excursions outside of the accepted range will be immediately reported to the Investigator, [name] and the study drug affected will be quarantined. Documentation of the excursion is to be recorded and sent to [name] by email or in person for review and determination of continued use of the study drug. [name] will consult with Red Leaf Medical.

Dosage and Administration (Day 1)

Once all Baseline Visit procedures are completed eligible participants will receive a 3 month supply of Uromune® treatment. Participants will be instructed to take 2 sprays of the treatment under their tongue, once daily for 3 months (90 days). The liquid is to be held under the tongue for 2 minutes without swallowing. After the 2 minutes has passed the liquid is to be swallowed. The Uromune® treatment is to be taken before breakfast each day to avoid mixing it with foods or beverages.

If a dose is missed, participants should take the dose as soon as they remember on the same day and inform the study staff. However, if it is the next day, the missed dose should be skipped and the next dose taken as normal. **Only one dose of study drug (2 sprays) should be taken each day** and a double dose should not be taken.

Study Treatment Compliance

Participant compliance with the study treatment will be assessed through a review of the participant's Treatment Diary during their 3 month clinic visit. At the 3 month clinic visit, the participant will return the study treatment bottle and any unused study treatment.

Drug Accountability

The investigator will be responsible for product accountability. Site staff will be required to maintain a drug accountability log throughout the duration of the study. These records shall include dates, quantities, batch numbers, and expiry dates, receipt date of study medication at site, dispense date of study drug to each participant and return date of each participants study drug.

Safety Reporting

The investigator is responsible for the detection and documentation of events meeting the criteria and definition of an AE or SAE. The research coordinator will record all clinical AEs, noted during the trial, on the AE event log, report to the Investigator, [name], and enter into the electronic data capture database (EDC). All adverse events will be reported to the ethics board as per local guidelines.

For this study, the following standard AE definitions are used:

Adverse Event (AE)

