An AE, also known as an adverse experience, is defined as any untoward medical occurrence in a patient or clinical investigation participant administered a pharmaceutical product and which does not necessarily have to have a causal relationship with this treatment (ICH GCP/Health Canada Division 5).

An AE can therefore be any unfavorable and unintended sign, symptom, abnormal results of an investigation, or disease (new or exacerbated) temporally associated with the use of the investigative product, without any judgement on causality

Events that do not meet the definition of an AE include:

- Medical or surgical procedures; the condition that leads to the procedure is an AE.
- Anticipated day-to-day fluctuations of a pre-existing disease or condition present at the start of the study that do not worsen.
- The disease/disorder being studied (eg. Recurrent urinary tract infections) or expected progression, signs or symptoms of the disease being studied, unless more severe than expected for the participant's condition.

AEs that are serious, unexpected and at least possibly related to study participation will be reported to the Research Ethics Board and to Health Canada within the timelines indicated below.

All other AEs such as those that are not serious, expected and not related to the study participation will not be reported to the local Research Ethics Board, as per local guidelines.

Serious Adverse Event Definition/ Reporting Requirements

An adverse event is considered serious if any untoward medical occurrence includes any of the following:

- a) Results in death: This includes any death that occurs while the participant is in the study.
- b) Is immediately life-threatening.
 When in the view of the Investigator, the AE places the participant at immediate risk of death. It does not include a reaction that had it occurred in a more severe form, might have caused death.
- c) Event requires in-patient hospitalization or prolongation of existing hospitalization.

In the absence of an AE, hospitalization or prolongation of hospitalization should not be reported as an SAE in the following circumstances:

- Hospitalization or prolongation of hospitalization is part of a routine procedure followed by the study centre.
- Hospitalization for survey visits or annual physicals.
- For hospitalization planned and documented before the start of the study for preexisting condition which has not worsened.
- d) Is a congenital anomaly/birth defect.

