Quality of life and satisfaction questionnaires will also constitute secondary endpoints

The analysis for both efficacy and safety will be an intent to treat analysis of all participants who took at least one dose of the Uromune®. A per protocol efficacy analysis will include all participants who completed the 3 month treatment regime.

Interim Analysis Plan and Stopping Rules

An interim analysis will be carried out when 50% of participants reach the 6month follow up interval. Stopping rules will be based on safety considerations – the study would be stopped if >20% (8 participants) experienced Treatment Emergent Serious Adverse Events (TESAEs). Safety will be monitored continuously for the rest of the study and the study will be stopped if at any time, if >20% of participants experience TESAEs.

Summary Statement: Rationale for this Investigator Initiated Early Experience Real Life Clinical Practice Study

We hope that this study will provide guidance for the use of Uromune® (when or if it is released in Canada) by providing information on the best way to manage recurrent UTI in individual participants using their own clinical data (in this case the number of recurrent UTI). The ultimate goal is to reduce participants' suffering (and therefore improve quality of life), participant time spent dealing with this problem, indirect costs (time off work or other activities), antibiotic use, antibiotic resistance and health care utilization (including costs). We plan to undertake this study with great enthusiasm with limited funding (and "in kind" supply of Uromune® from Red Leaf Medical) because of the huge unmet need for better preventative therapy for our Canadian women with recurrent UTI.

Responsibilities:

Principle Investigator ([name]) Responsibilities – will assume sponsor responsibilities: The PI ([name]) will be responsible for protocol development, diary and CRF development, IRB approvals, informed consent, inclusion/exclusion criteria confirmation, safety monitoring, data analysis, and presentation/publication of results..

Supplier (Red Leaf Medical) Responsibilities: Red Leaf Medical will be committed to providing Uromune® for 80 participants to be enrolled in the trial. The Supplier is not committed to provide funds to the investigator, [name] or provide any further financial support for the trial.

References:

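### As most naturally read, the protocol's only numerical safety stopping limit (more than 20% with TESAEs) starts at the 6-month interim, about 90 days or more after the first 40 women finish dosing; it should apply from first dose, with a minimum count

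*Combined protocol and SAP*

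**What the plan says.** The section Interim Analysis Plan and Stopping Rules has three steps.

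- Timing: "An interim analysis will be carried out when 50% of participants reach the 6month follow up interval".
- Rule: "the study would be stopped if >20% (8 participants) experienced Treatment Emergent Serious Adverse Events (TESAEs".
- Continuation: "Safety will be monitored continuously for the rest of the study". The second half of that sentence attaches the same limit to this later phase: "the study will be stopped if at any time, if >20% of participants experience TESAEs".

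The 6-month point is counted from baseline (6 Month Phone Call: "Participants will be contacted by phone 6 months after their baseline visit"). The vaccine is taken "once daily for 3 months (90 days" from Day 1 (Dosage and Administration). The Early Termination section allows the study to be stopped "based on planned protocol interim analysis and/or stopping rules".

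Other safety provisions run from the start:

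- observed first dose and coordinator contact within a week of starting (Risk Mitigation);
- notification of serious events to the investigator, monitor and safety lead within 24 hours (the section on SAE review and its potential impact on the trial);
- safety-lead assessment of serious events (Risk Mitigation);
- monthly aggregate review of adverse events, supported by statistician reports (Study Monitoring);
- expedited reports to Health Canada in 7 or 15 days (Governing Regulatory Authorities);
- reporting of events that are "serious, unexpected and at least possibly related to study participation will be reported to the Research Ethics Board" (Adverse Event definition);
- discretionary suspension or termination for safety (SAE review section; Termination of the Study).

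None of these has a numerical trigger.

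**The concern.** A numerical stopping limit protects participants most while they are being exposed. Here the rule is introduced at the interim, its count of 8 is 20% of the 40 women who define the interim, and the continuous phase covers what remains of the study after that look. Read in that order, the limit is not in force while the first 40 women are on drug, or for about three months after the last of them finishes.

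The investigator also carries the sponsor's responsibilities and decides on further action after discussion with the safety lead. A limit fixed in advance is useful in that position because it does not depend on judgement at the time. Early onset is also plausible: the one serious reaction the protocol lists, a severe rash, began within 2 days of starting treatment.

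**Working it through.** **Inputs.** 80 women planned (Number of Participants); interim at 50% reaching 6 months; threshold above 20%, given as 8 participants; 90 days of dosing; 6 months from baseline, within 7 days either way. The protocol gives no accrual rate and no expected TESAE rate, so both are assumed below.

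**1. The plan's own figure.** 50% × 80 = 40, and 20% × 40 = 8. The 8 therefore belongs to the interim denominator. Strictly, 8/40 is exactly 20%, so *more than* 20% of 40 needs 9. The difference matters a little: at a true 10% rate, P(≥9 of 40) = 1.5% and P(≥8 of 40) = 4.2% (exact binomial).

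**2. The gap.** 6 months is 180 to 183 days; minus 90 days of dosing, this leaves 90 to 93 days (83 to 100 with the visit window). That is for the 40th woman to reach 6 months. For women enrolled before her it is longer.

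**3. Dosing already delivered at the interim.** Assume uniform accrual over A months and a 3-month course. The interim falls at T = A/2 + 6. Started = 80 × min(1, T/A). Finished = 80 × min(1, (T − 3)/A). On drug = started − finished. Share delivered = (finished + on drug/2)/80.

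| A (months) | T | Finished | On drug | Not started | Share delivered |
|---|---|---|---|---|---|
| 6 | 9 | 80 | 0 | 0 | 80/80 = 100% |
| 12 | 12 | 60 | 20 | 0 | 70/80 = 87.5% |
| 24 | 18 | 50 | 10 | 20 | 55/80 = 68.75% |

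**4. Why a minimum count is needed.** A bare running limit of more than 20%, checked after each woman, is crossed by one event among the first 1 to 4 women. An exact recursion gives the chance of crossing by 40 women as 8.2% at a 2% rate and 21.1% at a 5% rate.

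**5. Chance of an unneeded pause.** Simulation: monthly looks from first dose, all women dosed as denominator, A = 6, 12 or 24, evenly spaced or random accrual, onset within 2 days or spread over 90 days.

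| Minimum events | 5% rate, maximum | 10% rate, range |
|---|---|---|
| 3 | 2.8% | 0.4% to 17.5% |
| 4 | 1.3% | 0.3% to 12.7% |
| 5 | 0.6% | 0.3% to 9.5% |

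Repeat runs with a minimum of 5 reached 9.9% at the 10% rate, so about 10% is the fair upper figure. At a 2% rate the chance was at most 0.01%. The written rule, from the interim onward on the same all-dosed denominator, fires with chance 0.2% to 1.3% at the 10% rate. At the maxima the ratio is 9.5/1.3, about 7.

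**6. Possible benefit, illustrative only.** Assume a true 30% rate, onset spread over 90 days, evenly spaced accrual, a pause that becomes permanent, and no earlier discretionary action. The mean share of planned dosing delivered for A = 6, 12 and 24 is:

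- as written: 100%, 88% and 70%;
- from first dose with a minimum of 5: about 60%, 37% and 27%.

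**The case against.** The strongest reply is that this is a matter of wording. The final sentence says *at any time*, the Early Termination section joins the interim and the stopping rules with and/or, and the study is monitored in real time throughout. A site could apply the limit from the start. That reading is possible and cannot be excluded, but no text gives an earlier start date, and a stopping rule should not have two. If first dose was intended, writing it down costs nothing, and a minimum count would still be needed.

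Second, early safety is well covered. Three roles review events monthly, serious events are notified within 24 hours, and the investigator may suspend or stop. Those reviews would be expected to act before 20% of women had a serious event. This stands, and it limits the size of the point.

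Third, the benefit appears only at rates the documents do not suggest. The protocol lists the serious reaction at under 2%, and the cited UK experience had one treatment-related rash. At a 2% rate neither version of the rule would practically ever fire. This also stands.

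A reader might infer that women are dosed without safety oversight until the interim, or that the limit can protect nobody. The documents support neither. Oversight exists from first dose and only the numerical trigger is late. At the interim the limit can still act on women who are on drug or not yet started, if accrual is slow enough to leave any.

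**Conclusion.** The point holds as a modest gap in a pre-specified trigger. On the natural reading, the only numerical safety limit is inactive throughout dosing of the first 40 women and for about 90 days or more afterwards. The 40 women and the 90 days follow directly from the protocol. The start date rests on reading the continuous phase as beginning at the interim, so confidence is moderate.

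The share of dosing delivered by then (69% to 100%) depends on assumed accrual of 6 to 24 months. The reduction in exposure at a 30% TESAE rate shows how the rule would behave and is not a forecast. The case for change is that a limit the protocol already chose should operate during exposure, and that the change is cheap. It does not rest on any sign that the vaccine is unsafe.

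**What to change.** Amend Interim Analysis Plan and Stopping Rules to state that:

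- the limit of more than 20% with TESAEs applies from first dose and is checked at each monthly aggregate review already planned under Study Monitoring;
- the denominator is all women dosed, and at least 5 women must have a TESAE before the limit can be crossed;
- before the interim, crossing pauses new and ongoing dosing pending review by the investigator and safety lead;
- at and after the 6-month look the stop is kept, with the count corrected to 9 of 40, or the rule restated as at least 20% if 8 was intended.

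The 20% level itself need not move, and no new visits, data or committee are required. The price is the chance of an unneeded pause set out in step 5 of the working. A pause may also interrupt some 90-day courses, and completing the course defines the per-protocol set, so the amendment should say how interrupted courses are handled. A minimum of 3 or 4 is possible but raises the chance of an unneeded pause.

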- e) Results in persistent or significant disability or incapacity.
- f) Is an important medical event that may jeopardize the patient or may require medical intervention to prevent one of the outcomes listed above.

Recording Adverse Events

All adverse events, which include any detrimental change in the participant's condition, will be collected from the time the participant signs the consent form until the follow up period is completed at the 12 month clinic visit.

AEs will be captured wherever possible as a diagnosis and it is the Investigator's responsibility to ensure this is done. All AEs including SAEs are to be accurately recorded on the Adverse Event case report form(s). The Investigator will carefully evaluate each AE to determine severity, expectedness, relatedness and outcome as indicated below.

Severity:

- Grade 1 Mild: Participant is aware symptoms but they are easily tolerated and have no or mild impact on regular activities. Symptoms do not require medical attention or treatment.
- Grade 2 Moderate: An event the participant experiences that is of minor concern or convenience. These events may have an impact on Page 12 of 24

daily activities but can typically be improved with simple therapeutic measures. These experiences may interfere with the participant's normal functioning.

- Grade 3 Severe: These events are usually incapacitating to the participant. They impact normal daily activities and typically require treatment or systemic drug therapies.
- Grade 4: Life threatening or disabling.
- Grade 5: Death

Expectedness

AEs must be classified based on whether or not they were expected given current knowledge of the study treatment and procedures:

- Unexpected: The event is not expected based on current information of the condition or the study treatment as outlined in the protocol, investigator's brochure or consent form. Is considered for expedited reporting purposes when the type or event or severity of the event is not listed in the current IB.
- *Expected:* The event is known to be associated with the condition being studied or the intervention.

Expected AES

Expected transient AEs associated with treatment reported occurrence <10%.

- Post nasal drip
- Stinging around mouth
- Pruritus over old BCG scar
- Pruritus over abdomen
- Intermittent abdominal pain
- Mild nausea
- Asthma exacerbation

Serious Adverse Event

Reported occurrence <2%.

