
Protocol Deviations

The study is to be conducted as described in the protocol without deviation unless there is a safety concern. The protocol must not be modified for any participant without the prior consent of the Research Ethics Board responsible at the investigative site.

Termination of the Study

If the Investigator discovers conditions during the course of the trial that indicate that the study should be discontinued an appropriate procedure for termination will be instituted.

Reasons for closure of the trial or termination of the study by the Investigator may include the following:

- Successful completion of the study at study site.
- Failure of Investigator to comply with the protocol, GCP guidelines or regulatory requirements
- Safety concerns

Rationale for Study Design

It would be difficult and really impossible to undertake a large multicenter randomized placebo controlled prophylaxis trial with limited funding. The need for evaluation of this type of intervention in Canadian female patients is unquestionable and the general efficacy and safety of Uromune® in Canadian women can be assessed using an open label real life observational study design employing using each participant's history of UTI as their own individual control. We will be able, within the number of participants planned for enrollment (convenience sample based on the number of individual Uromune® doses to be provided by supporting company) to answer our aim: To determine if Uromune therapy provides a clinically acceptable (efficacy and safety) prophylactic option in lieu of continuous and/or interval antibiotic dosing for Canadian women with a history of recurrent UTI.

We do not want to prove that this intervention is better than other interventions (in fact there are no other real non-antibiotic alternatives) but rather reduce the risk of recurrent UTI in women who are suffering from multiple UTIs requiring antibiotics. Each individual participant will be their own control based on the number of UTIs that are documented over the previous 12 months (to be included participants must meet the criteria of 3 documented UTIs requiring antibiotics over the last 12 months or 2 UTIs requiring antibiotics over the previous 6 months).

Number of Participants: Inmunotek, through its Canadian distributor, has offered the principle investigator at no cost, vaccine product (Uromune®) to treat up to 80 participants. The number of participants enrolled will be a convenience

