sample based on the early UK experience [2]. It is expected that 80 participants in total (with an expected drop out rate of 15%) enrolled at the Urology Centre at Queen's University site will allow a preliminary assessment of efficacy and safety. The UK early experience study reported that 78% (59 participants of a total of 75 evaluable participants) had no subsequent UTI in the 12 months after the vaccine was administered. One participant reported a treatment related rash while <10% of participants experience mild adverse reactions with only one participant temporarily suspending treatment. We anticipate that based on this experience, 80 participants will be sufficient to determine safety and potential efficacy.

Analysis

Primary outcome: The individual participant will be considered a complete responder if they have no UTI requiring antibiotics reported in the 12 months since initiating therapy. A 50% responder rate of all enrolled participants will be considered a very clinically significant result. Based on the results from the first experience report from the UK (Yang and Foley, 2017) with Uromune® which demonstrated that 78% of the 75 women who completed treatment had no subsequent UTIs in the follow-up period, our convenience sample should be sufficient to power our analysis. The primary efficacy endpoint will be considered to have been achieved if a clinically significant and important level of more than 50% of participants undergoing therapy has no reported UTI in the 12 months after initiation of therapy.

Secondary outcome: The number of UTI in individual participants requiring antibiotics in the 12 months after starting therapy will be compared to the number of UTIs requiring antibiotics before therapy is initiated (number over previous 12 months or 2 X the number over the preceding 6 months). The analysis will include individual participant data comparisons as well as the mean number of UTI before and after initiation of therapy in the entire cohort. Based on the results from the comparison of Uromune® vs antibiotics from Spain (Lorenzo-Gomez MF et al 2012) which demonstrated a mean UTI rate after Uromune® therapy (n=136) of 0.36 (CI0.29-0.44) at 6 months, 0.72 (CI 0.60-0.85) at 9 months, the study should be adequately powered to show a statistically significant difference in our convenience sample of participants enrolled with a history of at least 3 UTI in the preceding 12 months.

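### The interim safety boundary gives no single answer at exactly 8 participants with serious events, because 8 of the derived 40 is 20.0% and the rule asks for more than 20%

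*Combined protocol and SAP*

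**What the plan says.** The rule is in the protocol's section Interim Analysis Plan and Stopping Rules.

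- Timing: "An interim analysis will be carried out when 50% of participants reach the 6month follow up interval".
- Interim boundary: "the study would be stopped if >20% (8 participants) experienced Treatment Emergent Serious Adverse Events (TESAEs").
- After the interim: "the study will be stopped if at any time, if >20% of participants experience TESAEs". The strict inequality is repeated, with no count.

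Two other places bear on the denominator. Number of Participants states "It is expected that 80 participants in total", with product supplied "to treat up to 80 participants". The Analysis section, just above the stopping rule, bases the efficacy and safety analyses on "all participants who took at least one dose" of the vaccine.

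The protocol does not print the number of participants at the interim, and it does not say whether the bracket means 8 or more, or more than 8. Termination of the Study lists safety concerns as a ground for closure but gives no number.

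**The concern.** A numerical stopping rule should lead any two people with the same count to the same decision. Here the boundary is written twice in one phrase, as a percentage and as a number of participants, and at the planned sample size the two part company at one value. Someone who works from the printed 8 would stop the study at 8. Someone who works from the inequality would continue and wait for a ninth.

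Under Study Monitoring, the study monitor, the investigator and the safety lead review adverse events together each month. If the count landed on 8, they would have to decide what the rule meant after seeing the data, and a pre-specified threshold exists to avoid that.

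**Working it through.** **Inputs.** Planned enrolment 80 (Number of Participants). Interim at 50% of participants, boundary above 20%, bracketed count 8 (Interim Analysis Plan and Stopping Rules).

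**Reproducing the printed count.** Interim number = 0.50 × 80 = 40. Twenty per cent of it = 0.20 × 40 = 8.0. The printed 8 is therefore exactly 20% of 40, which is very probably where it came from.

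**Testing it against the inequality.**

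- 8/40 = 0.200, which is not greater than 0.20.
- 9/40 = 0.225, the first count that is greater.

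So *above 20%* starts at 9 of 40, and *at least 20%* starts at 8 of 40. The two differ only when the count is exactly 8.

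**How often the disputed count would occur.** Take X as binomial with n = 40 and true TESAE risk p. Then P(X = 8) = C(40, 8) × p^8 × (1 − p)^32, which equals P(X ≥ 8) − P(X ≥ 9). The protocol gives no all-cause TESAE risk, so every row is an assumption.

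| Assumed p | P(X ≥ 8) | P(X ≥ 9) | P(X = 8) |
|---|---|---|---|
| 5% | 0.07% | 0.01% | 0.06% |
| 10% | 4.2% | 1.6% | 2.6% |
| 15% | 24.4% | 13.5% | 10.9% |
| 20% | 56.3% | 40.7% | 15.6% |
| 25% | 81.8% | 70.0% | 11.8% |
| 30% | 94.5% | 88.9% | 5.6% |

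Of these rows, the disputed count is most likely at a true risk of 20%, the boundary itself.

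**Dependence on the denominator.** If the rule is applied to everyone dosed, more than 40 may have started treatment by the time 40 reach six months. Eight is then below 20%: 8/41 = 19.5%, and 8/80 = 10.0% if all 80 have been dosed. With 80 dosed, *at least 20%* means 16 (0.20 × 80) and *above 20%* means 17 (17/80 = 21.3%). A count of 8 or 9 therefore fits only n = 40.

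**The case against.** The strongest reply is that the bracket is a gloss: more than 20%, where 20% is 8. On that reading the sentence is consistent and stopping begins at 9. The exact match of 8 with 0.20 × 40 supports this, and so does the next sentence, which uses the percentage alone. This stands as a possible reading, so a flat contradiction is not proved. It does not remove the ambiguity, because 8 is the only count printed as the condition for stopping.

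Second, 40 is inferred. Enrolment is a convenience sample with supply for up to 80. Eight would be the correct first count above 20% for 35 to 39 participants (8/35 = 22.9%, with 7/35 = 20.0%; 8/39 = 20.5%), that is, with 70 to 78 enrolled. This is true, but the protocol expects 80.

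Third, other safeguards exist. Serious events go to the investigator, monitor and safety lead within 24 hours, the investigator reviews adverse events in real time, and the study can be suspended or closed on safety grounds. These do not settle what the rule says at 8, but they leave it little practical consequence.

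A reader might also infer that the effect is negligible because the protocol lists a serious event with "Reported occurrence <2"%. That figure belongs to one listed event, a severe rash. The stopping rule is not limited to that event or to related events, so the figure cannot stand in for the all-cause TESAE rate.

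**Conclusion.** The point holds as a minor defect of wording in a rule that the trial would act on. With 80 enrolled and the interim denominator taken as 40, the boundary has no single answer at exactly 8 participants with TESAEs, and nothing else in the protocol supplies one. The size is one participant. The chance that it matters at the interim runs from about 0.06% at an assumed true risk of 5% to 15.6% at 20%.

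A reader might go further and infer that participants are left unprotected, or that the investigators have plainly miscalculated. The documents support neither. Under either reading the study stops at 9 of 40, and safety oversight does not depend on this rule alone. The 8 is a correct 20% of 40; the fault is that it is attached to a strict inequality.

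**What to change.** Make the inequality and the count agree, in one of two ways:

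- *at least 20% (8 or more of 40)*, which keeps the printed count and is the safer choice because it stops one participant sooner; or
- *above 20% (9 or more of 40)*, which keeps the printed inequality.

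The investigator and safety lead should choose. Carry the same inequality into the continuous-monitoring sentence. State that the interim count applies to the 40 who reached six months. If the at-least-one-dose set is preferred, cross-refer to its definition in the Analysis section and compute the count from the number dosed at that date.

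The cost is a one-line correction and a statement of the denominator, reported to the Research Ethics Board as a protocol change. No new data, visits or analyses are needed.
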